APPENDIX A

Response Criteria and Survival Outcome Definitions

Timing of Response Evaluation

Response will be evaluated according to the Schedule of Evaluations listed above (Section 6.0)

Definition of Measurable Disease

- a. Measurable protein criteria of the serum are defined as serum M-protein of IgG, IgA, IgD, IgE Isotype ≥ 1.0 gm/dl (10.0 g/L). Measurable protein criteria of the urine are defined as urine M-protein (Bence-Jones Protein) > 200 mg/24 hours.
- Participants with IgM peaks must have either ≥ 20% bone marrow plasmacytosis or >3 lytic lesions on skeletal survey.
- c. Non-Secretory Disease: Participants without quantifiable M-proteins but with ≥20% bone marrow plasmacytosis will be assessed using plasma cell percentages. These participants will be evaluated for CR, no CR, and progression/relapse using the criteria above.

Response Criteria:

Multiple Myeloma: For the purpose of establishing one set of criteria for both Phase II and Phase III multiple myeloma studies, the following definitions will be used. These definitions are based on the International Uniform Response Criteria for Multiple Myeloma.

- a. **Measurable Disease**: Measurable, quantifiable protein criteria must be present. Acceptable protein criteria are:
 - Serum M protein ≥ 1 g/dL (≥ 10 g/L), quantified by using densitometry on serum protein electrophoresis (SPEP).

AND / OR

Urine M protein [Bence-Jones Protein] ≥ 200 mg/24 hrs (≥ 0.2 g/24 hrs), quantified by 24-hour urine protein electrophoresis (UPEP).

OR

 Patients who have both serum M protein levels < 1 g/dL AND urine M protein levels < 200 mg/24 hrs at baseline may be followed by serum free light chain (FLC) assay if involved free light chain level ≥ 10 mg/dL (≥ 100mg/L).

Oligosecretory and Non-secretory Disease: Patients that do not meet the criteria for measurable disease above may only be assessed for the following objective statuses: Stringent Complete Response, Stable, and Progression.

b. Objective Status:

Stringent Complete Response (sCR):

- Meets all of the criteria for Complete Response (CR) and
- normal serum free light chain ratio and

absence of clonal cells in bone marrow by immunohistochemistry or immunofluorescence **Complete Response (CR)**:

- Disappearance of all evidence of serum and urine M proteins on immunofixation electrophoresis studies and
- ≤ 5% plasma cells in bone marrow *and*
- disappearance of any soft tissue plasmacytomas

Very Good Partial Response (VGPR):

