- Meets all of the criteria for Partial Response (PR) and
- Serum and urine M proteins detectable by immunofixation but not on electrophoresis or
- ≥ 90% reduction in serum M protein **and** urine M protein < 100 mg/24 hrs.

Partial Response (PR):

- If the patient had soft tissue plasmacytomas present at baseline and they were assessed at this disease assessment: ≥ 50% reduction in size of soft tissue plasmacytomas (see Appendix A; Notes h.)*and*
- If the patient had ≥ 30% plasma cells in bone marrow at baseline and a bone marrow biopsy was done: ≥ 50% reduction in plasma cells **and**
- ≥ 50% reduction in serum M protein **and** reduction in urine M protein ≥ 90% or to < 200 mg/24hr **or**
- If patient had serum M protein < 1 g/dL, urine M protein < 200 mg/24 hrs, and an involved serum free light chain level ≥ 10 mg/dL at baseline: ≥ 50% decrease in the difference between involved and uninvolved serum free light chain levels

Stable Disease (STA):

• Patient does not meet criteria for Stringent Complete Response, Complete Response, Very Good Partial Response, Partial Response, or Progression.

Progression (PROG): Any one or more of the following:

- Serum M protein increase ≥ 25% from baseline (or an increase of ≥ 1 g/dL if serum M protein was ≥ 5 g/dL at baseline), with an absolute increase of ≥ 0.5 g/dL or
- Urine M protein increase ≥ 25% from baseline, with an absolute increase of ≥ 200 mg/24 hrs or
- If patient had serum M protein < 1 g/dL, urine M protein < 200 mg/24 hrs, and an involved serum free light chain level ≥ 10 mg/dL at baseline: ≥ 25% increase in the difference between involved and uninvolved serum free light chain level, with an absolute increase of ≥ 10 mg/dL or
- Bone marrow plasma cell percentage increase ≥ 25% from baseline, with the absolute plasma cell % ≥ 10% or
- New bone lesions or soft tissue plasmacytomas, or definite increase in size of existing bone lesions or soft tissue plasmacytomas (see Appendix A: Notes h.) or
- Development of hypercalcemia (corrected serum calcium > 11.5 mg/dL or 2.65 mmol/L) that can be attributed solely to multiple myeloma

NOTE: If a disease assessment indicates that a patient is experiencing a Stringent Complete Response, Complete Response, Very Good Partial Response, Partial Response, or Progression, this should be confirmed by a second disease assessment and this should be done prior to the institution of any new therapy. The second disease assessment may be done at any time.

Notes:

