- a. "M protein" may also be known by the following synonyms: M-spike, monoclonal protein, myeloma protein, monoclonal paraprotein, M-component.
- b. Urine M protein measurement is estimated using 24-hour urine protein electrophoresis (UPEP) only. Random or 24 hour urine tests measuring kappa and lambda light chain levels are not reliable and are not recommended.
- c. Patients with 'measurable disease' in both the serum and urine (serum M protein ≥ 1g/dL and urine M protein ≥ 200 mg/24h) at baseline need to be followed by both SPEP and UPEP for response assessment.
- d. Except for assessment of Complete Response, patients with 'measurable disease' restricted to the serum (serum M

protein \geq 1 g/dL and urine M protein < 200 mg/24h) at baseline may be followed by SPEP only. Likewise, except for assessment of Complete Response, patients with 'measurable disease' restricted to the urine (serum M protein < 1 g/dL and urine M protein \geq 200 mg/24h) at baseline may be followed by UPEP only.

- e. Patients with serum M protein ≥ 1 g/dL and/or urine M protein ≥ 200 mg/24h at baseline will be assessed for response based on SPEP and/or UPEP results only. Except for assessment of Stringent Complete Response, serum free light chain (FLC) assay response requirements are only applicable to patients who had serum M protein < 1 g/dL, urine M protein < 200 mg/24 hrs, and an involved serum free light chain level ≥ 10 mg/dL at baseline. A normal serum free light chain ratio is required for all patients for a Stringent Complete Response.
- f. To qualify for a Complete Response, both serum and urine immunofixation must be carried out and must be negative, regardless of the size of the baseline M protein in the serum or urine.
- g. Skeletal survey is not required for assessment of response unless clinically indicated, but is recommended once a year in clinical practice. Stringent Complete Response, Complete Response, Very Good Partial Response, Partial Response, and Stable Disease all require no known evidence of progressive or new bone lesions if radiographic studies were performed, but radiographic studies are not required to satisfy these response requirements.
- h. The size of the soft tissue plasmacytomas is defined as the sum of the products of the cross-diameters of each plasmacytoma. The size of the bone lesions will be determined in a similar manner. A definite increase in the size is defined as a ≥ 50% increase (and at least 1 cm²) of this sum.

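### Appendix A sets no free light chain criterion for VGPR or CR in patients measurable only by serum free light chain, so neither grade follows their light-chain response

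*Combined protocol and SAP*

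**What the plan says.** All the rules are in Appendix A.

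- **Who is followed by FLC.** A patient with serum M protein below 1 g/dL and urine M protein below 200 mg/24 h at baseline "may be followed by serum free light chain (FLC) assay if involved free light chain level ≥ 10 mg/dL". Section 5.1 sets no M-protein threshold, so such patients can enrol.
- **PR.** For these patients the criterion is "≥ 50% decrease in the difference between involved and uninvolved serum free light chain levels". Any applicable plasmacytoma and marrow conditions also apply.
- **Progression.** The FLC difference must rise by at least 25%, with an absolute rise of at least 10 mg/dL.
- **VGPR.** PR must be met, plus one of two M-protein conditions. The first is "Serum and urine M proteins detectable by immunofixation but not on electrophoresis". The second is a fall of at least 90% in serum M protein with urine M protein below 100 mg/24 h. Neither mentions FLC.
- **CR.** The first item is "Disappearance of all evidence of serum and urine M proteins on immunofixation electrophoresis studies". The other two are marrow plasma cells of at most 5% and no remaining soft tissue plasmacytoma. CR has no FLC item and does not require PR.
- **sCR.** CR plus a normal FLC ratio and no clonal marrow cells.
- **Notes e and f.** Apart from sCR, Note e says that "serum free light chain (FLC) assay response requirements are only applicable to patients who had serum M protein < 1 g/dL", with the matching urine and involved-FLC limits. Note f requires negative serum and urine immunofixation for CR. Neither note adds an FLC requirement at VGPR or CR.

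**The concern.** FLC is the assay that makes these patients measurable, yet two of their response grades ignore it. The added VGPR condition is meant to show a deeper response than PR. Where M protein was never visible on electrophoresis and immunofixation is positive, that condition already holds before treatment and so measures no change. Where a small spike persists, or immunofixation is negative with marrow above 5%, a deep FLC fall earns nothing beyond PR. For CR the FLC change plays no part.

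Sections 2.2 and 3.2 relate bone-marker and radiological change to myeloma response in 20 patients. If response depth enters that analysis, the same grade stands for different degrees of response in different patients.

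**Working it through.** The plan states no figure that depends on these rules, so there is none to reproduce. The check is to apply Appendix A as written to hypothetical patients.

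**Readings used.** The marrow and plasmacytoma conditions of PR apply to FLC-only patients too. The first VGPR condition is read as M protein seen on immunofixation but on neither serum nor urine electrophoresis. Nobody has plasmacytomas or meets a Progression criterion, and the FLC ratio stays abnormal, so sCR is not in play.

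**FLC-only patients.** Baseline involved FLC is 51 and uninvolved 1 mg/dL, so the difference is 51 − 1 = 50 mg/dL. Baseline marrow is 25%, below the 30% at which the PR marrow condition applies. Residual difference = 50 × (1 − fall).

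- A: no spike, immunofixation positive, follow-up marrow 15%
- B: no spike, immunofixation negative, follow-up marrow 15%
- C: no spike, immunofixation negative, follow-up marrow 4%
- D: serum spike 0.6 g/dL and urine 100 mg/24 h, both unchanged, follow-up marrow 15%

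| FLC fall | Residual (mg/dL) | A | B | C | D |
|---|---|---|---|---|---|
| 0% | 50 | stable | stable | CR | stable |
| 30% | 35 | stable | stable | CR | stable |
| 50% | 25 | VGPR | PR | CR | PR |
| 70% | 15 | VGPR | PR | CR | PR |
| 90% | 5 | VGPR | PR | CR | PR |

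**Serum-measurable comparison.** Baseline serum M protein is 3.0 g/dL and the spike stays visible. Residual = 3.0 × (1 − fall).

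| Serum fall | Residual (g/dL) | Grade |
|---|---|---|
| 50% | 1.5 | PR |
| 70% | 0.9 | PR |
| 89% | 0.33 | PR |
| 90% | 0.3 | VGPR |

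**What follows.**

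1. In A, VGPR begins at the PR threshold: falls of 50% and 90% get the same grade.
2. In B and D, a 90% fall stays at PR because neither VGPR condition can be met.
3. In C, the grade is CR at every fall, including none.
4. The requirement for two sequential assessments does not correct A. While immunofixation stays positive and electrophoresis negative, the second assessment gives the same grade.

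**The case against.** The other side has several good points.

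- **sCR.** A reader might infer that nothing above PR looks at light chains. That is wrong: sCR needs a normal FLC ratio in all patients. The gap is at VGPR and CR only.
- **How many patients.** A reader might infer that many FLC-only patients would be over-graded. The documents give neither their number nor the share who are immunofixation-positive and electrophoresis-negative. Any percentage would rest on an assumed distribution of FLC change. Patients like B and D show that the error can also run downwards.
- **Serum patients.** A reader might infer that they must always show a 90% fall. They may also use the electrophoresis route. For a patient with a visible baseline spike, however, that route requires the spike to clear, which is a real change.
- **Schedule.** Sections 6.2 and 7 list serum immunofixation only as an and/or item with urine beta-2-microglobulin. A Section 7 footnote restricts that item further, and no urine immunofixation is listed. How often these grades could be assigned is therefore uncertain. This limits frequency but does not repair the rule.
- **CR is narrow.** It also needs marrow of at most 5% and no plasmacytoma, and Section 6.3 takes marrow only at baseline and end of study. Against that, Appendix A records unconfirmed CR on serum and urine studies, with marrow only if drawn.
- **Intent.** Note f makes immunofixation the CR test whatever the baseline M protein, which may be deliberate. The documents do not show whether the appendix departs from the criteria it is based on, and this point does not claim that it does.
- **Impact.** A VGPR-or-better rate is not an endpoint, and Section 9.1 does not say how response is grouped. If patients were split at PR, moving A from PR to VGPR would change nothing. Patient C would still matter: with a fall of 0% or 30% the grade is CR rather than stable, which crosses that split.

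**Conclusion.** The point holds for VGPR and CR. For patients measurable only by FLC, Appendix A can grade a 50% fall in the FLC difference as VGPR, hold a 90% fall at PR, and assign CR with no fall. These results follow from the wording, given the stated readings and the immunofixation, electrophoresis, marrow and plasmacytoma findings specified.

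How often this would happen cannot be derived from the documents. For scale only, if 10% to 20% of the 20 patients were FLC-only (an assumption with no source in the plan), that would be 0.10 × 20 = 2 to 0.20 × 20 = 4 patients, and not all would be misgraded.

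A reader might infer that the trial's main result is at risk. It is not: the primary endpoint is change in serum osteocalcin, and neither it nor the stated 88% power uses response grades. The effect is confined to the exploratory secondary association between bone changes and myeloma response. The correction is worth making because it is specific and cheap.

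**What to change.** In Appendix A, for patients measurable only by FLC:

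1. **VGPR.** Keep the requirement to meet PR. Replace both M-protein conditions with a decrease of at least 90% in the involved-minus-uninvolved FLC difference, parallel to the plan's own 90% serum rule.
2. **CR.** Keep the present items and add an explicit FLC condition, at least the VGPR one above. A normal FLC ratio is an option, but it already helps separate sCR from CR. Moving it into CR would leave absence of clonal marrow cells as the only difference in these patients.

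With these changes, patients A, B and D would be stable at falls of 0% and 30%, PR at 50% and 70%, and VGPR at 90%. Patient C would be stable, stable, PR, PR and CR.

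The cost is two lines of text. Serum free light chains are already scheduled at baseline, during the treatment cycles and at end of treatment, so no new test is needed. VGPR and CR counts may become slightly less favourable, although patients like B and D could move up.

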Increasing Disease (INC): First objective status recorded (other than Unknowns or those before three weeks) of Progression, provided this occurs within eight weeks of registration.

Inadequate Assessment. Response Unknown (NASS): Progression greater than eight weeks after registration and either all objective statuses prior to registration are unknown or the only known objective statuses occurred less than three weeks after registration.

Relapse: In patients with a confirmed response as described above, relapse is defined as the first occurrence of any of the following, reconfirmed by repeat analysis of serum and/or 24-hour urine M protein, done more than 2 weeks apart:

- a. Myeloma protein increase by more than 100% from the lowest level recorded on study, or a rise of 2.0 g/dl (this increase must be to a level > 1.0 g/dL if it is to constitute the sole manifestation of relapse).
- b. Myeloma protein increase above the response criteria for PR (see criteria for Partial Remission).
- c. Reappearance of M-protein in blood or urine not related to immune recovery or recent infection.
- d. Increase in the size and number of lytic bone lesions recognized on radiographs. New skeletal or MRI lesions, preferentially confirmed by fine needle aspirate.
- e. Myeloma related cytogenetic abnormalities.
- f. BM plasmacytosis > 10% or > 5% light chain restricted, non-diploid, plasma cells on clg/DNA.
- g. Hypercalcemia, not explained by any other cause.

Survival Outcomes

Overall Survival: measured as the time from initial registration to death from any cause.

Event-Free Survival: measured as the time from initial registration to progression/relapse of disease or death from any cause

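### Appendix A measures M-protein Progression from baseline, so a clear rise from the lowest on-study value can be classed Stable or still PR, with no express rule to stop

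*Combined protocol and SAP*

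**What the plan says.** **Progression (Appendix A, Objective Status).** The serum limb is "Serum M protein increase ≥ 25% from baseline", with an absolute rise of at least 0.5 g/dL (for a baseline of 5 g/dL or more, a rise of at least 1 g/dL replaces the percentage). The urine and marrow limbs also refer to baseline. The light-chain limb asks for a "≥ 25% increase in the difference between involved and uninvolved serum free light chain level" and gives no reference point.

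**Other statuses.** The serum part of PR is "≥ 50% reduction in serum M protein", and nothing withdraws PR when the value is climbing again. Stable is what is left over: "Patient does not meet criteria for Stringent Complete Response, Complete Response, Very Good Partial Response, Partial Response, or Progression".

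**Confirmation.** Response and Progression should both be confirmed, but "The second disease assessment may be done at any time".

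**Relapse (Appendix A).** This is a separate event, limited to patients with a confirmed response and reconfirmed by repeat analysis more than 2 weeks apart. Item a is "Myeloma protein increase by more than 100% from the lowest level recorded on study", or a rise of 2.0 g/dL; the level must exceed 1.0 g/dL if this is the only sign. Item b is "Myeloma protein increase above the response criteria for PR". Item c is "Reappearance of M-protein in blood or urine not related to immune recovery or recent infection".

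**Stopping.** Section 4.1 requires discontinuation for progressive disease or unacceptable toxicity. Sections 4.1, 4.3 and 6 also allow for some other reason. Section 8.2.6 gives the investigator a right to withdraw patients for listed reasons, including progressive disease. None of these names Relapse or a rise from the lowest value. Appendix A pairs progression with relapse in its event-free survival definition; the stopping text does not.

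**The concern.** A patient's M-protein can fall on treatment and then climb well above its lowest value without passing the baseline-based threshold. Appendix A then records Stable or PR, and whether the patient stops depends on how the physician reads progressive disease.

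Two things are at stake. While on study, section 8.2.3.5 bars other anti-myeloma treatment, bisphosphonates and radiotherapy, so a patient with rising disease stays under those limits until someone decides to stop. And the primary endpoint is the change in osteocalcin to study exit (section 3.1), with the exit visit taking place at discontinuation (sections 4.1 and 6). How the physician reads the term therefore also sets when the primary measurement is taken.

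**Working it through.** The plan gives no figure to reproduce here, so the check applies the Appendix A rules to example patients. All M-protein values are assumed, in g/dL, and the urine, marrow, lesion, plasmacytoma and calcium criteria are taken not to change the status.

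**Current thresholds, baseline 4.0**
- Progression starts at max(1.25 × 4.0, 4.0 + 0.5) = max(5.0, 4.5) = 5.0.
- PR holds up to 0.5 × 4.0 = 2.0.

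**Threshold if measured from the lowest value L (L below 5):** max(1.25 × L, L + 0.5).

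| Case | Baseline / lowest / now | Change from lowest | Change from baseline | Status now | Relapse a or b | Threshold from lowest |
|---|---|---|---|---|---|---|
| 1 | 4.0 / 2.2 / 4.8 | 2.6/2.2 = +118% | 0.8/4.0 = +20% | Stable | cannot apply | max(2.75, 2.70) = 2.75 |
| 2 | 4.0 / 1.3 / 2.0 | 0.7/1.3 = +54% | −2.0/4.0 = −50% | PR | neither | max(1.625, 1.80) = 1.80 |
| 3 | 4.0 / 1.0 / 4.4 | 3.4/1.0 = +340% | 0.4/4.0 = +10% | Stable | a and b | max(1.25, 1.50) = 1.50 |
| 4 | 4.0 / 0.4 / 1.2 | 0.8/0.4 = +200% | −2.8/4.0 = −70% | PR | a | max(0.50, 0.90) = 0.90 |

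- **Case 1.** The best fall is (4.0 − 2.2)/4.0 = 45%, short of PR. There was no response, so Relapse cannot apply.
- **Case 2.** The value sits exactly at the PR limit. Item a needs more than 2 × 1.3 = 2.6, or a rise of 2.0; item b needs a value above 2.0. Neither is met.
- **Cases 3 and 4.** Appendix A already labels these Relapse if the response was confirmed and the rise reconfirmed. The stopping text does not refer to that label.

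None of the four is Progression today. All four would be if the same floors were applied to the lowest value.

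**Doses that could remain.** The plan is 6 cycles × 4 doses = 24. At the visit in week 4k, 4k doses have been given if none was missed or delayed, so 24 − 4k remain. With scheduled visits only, a fall can first be seen at week 4 and a rise at week 8.
- Rise at week 8, confirmed at once: 24 − 8 = 16 of 24 (67%). This can occur in a patient with no response. It can also occur in a responder, because PR too may be confirmed at any time.
- Rise at week 8, confirmed at week 12: 24 − 12 = 12 of 24 (50%).
- Rise first seen at week 20 and confirmed at the end-of-treatment visit: 0.

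These are doses that could follow the rise if the physician does not stop for another reason. They do not predict what will be given.

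**The case against.** The strongest reply is that the appendix already has an event measured from the lowest value. Relapse covers a confirmed responder with a large rise, and event-free survival treats progression and relapse together. The stopping text uses the general term progressive disease, not the defined status, so a physician could read it to include Relapse. A physician who sees M-protein above baseline after a deep fall would hardly continue just because the status is Stable. In a six-cycle study with osteocalcin as its primary endpoint, treating on while M-protein is below baseline is defensible.

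Much of this stands, and it keeps the point small. It narrows the gap for cases 3 and 4. It does not close it for cases 1 and 2, which are not Relapse on any reading.

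It is also fair that the remedy moves some exits away from week 24 and could disturb the recorded response. That argues for stating precedence and disclosing the cost.

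A reader might infer that the protocol directs treatment to continue through relapse. It does not: it is silent, and it allows stopping for another reason. Nor is every relapse missed. New bone lesions, hypercalcemia attributed solely to myeloma, or a rise past the baseline threshold (5.0 in these examples) still count as Progression.

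**Conclusion.** The point holds as a gap in definition. A clear rise from the lowest on-study value can be recorded as Stable or PR, and no stopping rule expressly covers it. It is plainest for a patient never in response, and for a moderate rise in a responder.

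The size is modest. At scheduled visits, between 0 and 16 of 24 planned doses could follow the confirmed rise. The number of patients affected cannot be derived from the documents; with 20 enrolled and at most six cycles, it is likely to be few. The M-protein values are illustrations, but the classifications follow directly from the Appendix A wording.

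It may be tempting to conclude that the primary result is biased because exit timing varies. The documents do not support that: they establish neither a direction nor a size of effect on osteocalcin. Severity: worth considering.

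**What to change.** 1. **Appendix A.** Measure the M-protein, light-chain and marrow limbs of Progression from the lowest on-study value, or from baseline if there was no fall. Keep the percentage and absolute floors and the confirming assessment, and read the 5 g/dL clause against the same lowest value.
2. **Section 4.1.** State that confirmed Progression so defined requires discontinuation even if the value still meets PR or VGPR. An assessment meeting both counts as PR or VGPR for Best Response and as Progression for discontinuation. Without this, PR at 1.0 in week 4 followed by 1.6 in week 8 (baseline 4.0, threshold 1.5) is a confirmed PR today but would have no clear status.
3. **Relapse below that threshold.** Leave it to the physician. Items b and c have no absolute floor: with baseline 4.0 and lowest 1.95, a value of 2.05 meets item b after a rise of 0.10, whereas the threshold from lowest is max(2.4375, 2.45) = 2.45.

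**Cost.** Wording only. M-protein is already measured each cycle. Marrow is scheduled only at baseline and end of study, so that limb matters only if an extra sample is taken.

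**Downside.** A few patients would stop earlier and have exit osteocalcin measured before week 24, some well below baseline. With baseline 4.0 and lowest 1.0, Progression starts at 1.5, which is (4.0 − 1.5)/4.0 = 62.5% below baseline. A non-responder at 4.0 / 2.2 / 2.8 would stop (4.0 − 2.8)/4.0 = 30% below baseline and lose any later chance of response, which slightly affects the secondary response association. Event-free survival as Appendix A defines it would also be dated from the new Progression.

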APPENDIX C

Diagnostic and Staging Criteria

Diagnostic Criteria

Revised IMWG Diagnostic Criteria for Multiple Myeloma (Rajkumar, et al. 2014) Clonal bone marrow plasma cells ≥ 10% or biopsy-proven bony or extramedullary plasmacytoma^a And any one or more of the following myeloma defining events: Evidence of end organ damage that can be attributed to the underlying plasma cell proliferative disorder, specifically: Hypercalcemia: serum calcium >0.25 mmol/L (>1 mg/dL) higher than the ULN or 0 >2.75 mmol/L (>11 mg/dL) Renal insufficiency: CrCl <40 mL per min^b or SCr >177 µmol/L (>2 mg/dL) 0 Anemia: Hb >20 g/L below the LLN, or Hb <100 g/L 0 Bone lesions: one or more osteolytic lesions on skeletal radiography, CT, or PET-CT^c 0 Any one or more of the following biomarkers of malignancy: ○ Clonal bone marrow plasma cell percentage^a ≥60% Involved:uninvolved serum FLC ratio^d ≥100 0 >1 focal lesions on MRI studies^e 0 CrCl, Creatinine clearance; CT, computed tomography; FLC, free light chain; Hb, hemoglobin; Ig, immunoglobulin; IMWG, International Myeloma Working Group; LLN, lower limit of normal; M protein, monoclonal protein; MRI, magnetic resonance imaging; PET-CT, Positron emission tomography-computed tomography; ULN, upper limit of

^aClonality should be established by showing κ/λ –light-chain restriction on flow cytometry, immunohistochemistry, or immunofluorescence. Bone marrow plasma cell percentage should preferably be estimated from a core biopsy specimen; in case of a disparity between the aspirate and core biopsy, the highest value should be used. ^bMeasured or estimated by validated equations.

^cIf bone marrow has less than 10% clonal plasma cells, more than one bone lesion is required to distinguish from solitary plasmacytoma with minimal marrow involvement.

^dThese values are based on the serum Freelite assay (The Binding Site Group, Birmingham, UK). The involved free light chain must be ≥100 mg/L.

eEach focal lesion must be 5 mm or more in size.

Staging Criteria

International Staging system [ISS]

normal; SCr, serum creatinine

New International Staging System (Greipp, et al, JCO 2005)			
Stage	Criteria	Median Survival (months)	
I	Serum β2-microglobulin < 3.5mg/L Serum Albumin > 3.5 g/dL	62	
II	Not stage I or III	44	
111	Serum β2-microglobulin > 5.5 mg/L	29	

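### The hypercalcaemia limit for progression in Appendix A pairs 11.5 mg/dL with 2.65 mmol/L, which are different calcium concentrations

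*Combined protocol and SAP*

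**What the plan says.** The last item of the progression definition in Appendix A reads "Development of hypercalcemia (corrected serum calcium > 11.5 mg/dL or 2.65 mmol/L) that can be attributed solely to multiple myeloma". It is one of six items, any one of which is enough for progression. A note below the list says of a finding of progression that "this should be confirmed by a second disease assessment", with no fixed interval: "The second disease assessment may be done at any time".

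Appendix C, under the diagnostic criteria, also gives calcium in both units. It sets two alternative thresholds: "serum calcium >0.25 mmol/L (>1 mg/dL) higher than the ULN", and an absolute level of ">2.75 mmol/L (>11 mg/dL").

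On the origin of the response rules, Appendix A says: "These definitions are based on the International Uniform Response Criteria for Multiple Myeloma".

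Section 4.1 has patients leave the study on progression and attend the End of Treatment visit. The primary endpoint in Section 3.1 is the change in osteocalcin up to study exit.

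**The concern.** The two calcium figures read as one limit in two units, but they do not convert into each other. Nothing in the document says which one governs or in which unit calcium will be reported.

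Consider a patient who develops a corrected calcium between the two figures, attributed solely to myeloma and confirmed, and who meets no other progression criterion. Under the mmol/L figure the patient has progressed; under the mg/dL figure the patient has not. The choice can change three things:

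- the response category, which feeds the secondary endpoint on bone changes and anti-myeloma activity (Section 3.2);
- whether treatment stops;
- when the exit osteocalcin sample is taken.

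Calcium is part of the basic metabolic panel (Section 7, footnote 2), which Section 6.2 schedules at baseline, on day 1 of cycles 2 to 6 and at end of study. The criterion can therefore come into play repeatedly.

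The point is confined to this item. The separate relapse rule for confirmed responders, "Hypercalcemia, not explained by any other cause", carries no numeric limit.

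**Working it through.** **Inputs**

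- Appendix A, Progression: 11.5 mg/dL and 2.65 mmol/L.
- Appendix C, Diagnostic Criteria: 1 mg/dL paired with 0.25 mmol/L, and 11 mg/dL paired with 2.75 mmol/L.
- Assumed physical constant, used only as a cross-check: molar mass of calcium 40.078 g/mol.

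**Step 1: the conversion factor in each appendix**

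- Appendix C: 0.25 / 1 = 0.25 and 2.75 / 11 = 0.25 mmol/L per mg/dL, so its two pairs agree.
- Molar mass: 10 / 40.078 = 0.2495, which supports Appendix C.
- Appendix A: 2.65 / 11.5 = 0.2304, which is (0.25 − 0.2304) / 0.25 = 7.8% too low. It would need a molar mass of 11.5 × 10 / 2.65 = 43.4 g/mol.

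**Step 2: convert each figure**

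| Figure in Appendix A | Appendix C factor | Molar mass |
|---|---|---|
| 11.5 mg/dL | 11.5 × 0.25 = 2.875 mmol/L | 115 / 40.078 = 2.869 mmol/L |
| 2.65 mmol/L | 2.65 / 0.25 = 10.6 mg/dL | 2.65 × 40.078 / 10 = 10.62 mg/dL |
| Gap in mmol/L | 2.875 − 2.65 = 0.225 | 2.869 − 2.65 = 0.219 |
| Gap in mg/dL | 11.5 − 10.6 = 0.9 | 11.5 − 10.62 = 0.88 |

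Relative to 11.5 mg/dL the gap is 0.9 / 11.5 = 7.8% (0.88 / 11.5 = 7.7% by molar mass). Relative to 2.65 mmol/L it is 0.225 / 2.65 = 8.5% (0.219 / 2.65 = 8.3%).

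**Step 3: could rounding explain it?**

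- Values that round to 11.5 mg/dL run from 11.45 to 11.55, which is 2.8625 to 2.8875 mmol/L.
- Values that round to 2.65 mmol/L run from 2.645 to 2.655, which is 10.58 to 10.62 mg/dL.
- The ranges do not meet. If the factor 0.25 is itself treated as rounded (0.245 to 0.255), 11.5 mg/dL is 2.82 to 2.93 mmol/L, still well above 2.65.

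**Step 4: a check that needs no conversion**

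Set Appendix A beside the absolute level in Appendix C. In mg/dL the Appendix A limit is the higher of the two (11.5 against 11). In mmol/L it is the lower (2.65 against 2.75). Both pairs cannot be right.

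**Step 5: a literal *or***

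If the two figures are alternative limits, any value above 11.5 mg/dL is already above 2.65 mmol/L. The lower figure always decides and 11.5 mg/dL has no function.

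**The case against.** The mismatch itself is hard to dispute. The case on the other side is about weight and reading.

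- **The laboratory will probably use mg/dL.** The trial has 20 patients at one US institution, and the line puts mg/dL first, so 11.5 would probably be applied throughout. This is plausible, but it is an inference: no section states a reporting unit.
- **The affected group is narrow.** The value must be new, fall in the band, be attributed solely to myeloma, be confirmed, and occur without any of the other five criteria. This stands, and it is why the effect is probably small.
- **The primary analysis is barely touched.** End-of-treatment procedures are to be done at any withdrawal (Section 8.2.6), so the exit sample is planned under either limit and only its timing can move. The response association is exploratory (Section 9.1). This also stands.
- **A literal *or* gives a determinate rule.** Appendix C does use *or* between two different calcium thresholds. Elsewhere Appendix A gives an equivalent in parentheses after the figure, as in "involved free light chain level ≥ 10 mg/dL (≥ 100mg/L"), but that is weak evidence about intent, because the calcium pair is already inside parentheses. Equivalence is the more natural reading, and the literal one still leaves 11.5 mg/dL redundant.
- **The consequences are less fixed than progression versus stable disease.** A patient in the band might otherwise hold a partial or better response. Section 8.2.6 also words withdrawal for progression as the investigator's right, whereas Section 4.1 states that patients will be discontinued. Both are fair qualifications and neither reconciles the figures.
- **The mismatch may have been inherited from the published criteria.** The documents cannot show this. Investigators apply the protocol text, which conflicts with itself either way.

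**Conclusion.** The concern holds. As written, the Appendix A limit names two different concentrations, 0.225 mmol/L (0.9 mg/dL) apart on the protocol's own factor. Patients with corrected calcium above about 10.6 and up to 11.5 mg/dL are classified differently depending on the figure used. The conclusion rests only on the calcium pairs in Appendix C, and the molar mass agrees with it.

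This is a minor correction to a working decision threshold. The likely effect on results is small. It cannot be put as a number, because the documents give no rate of values in the band. The 88% power statement in Section 9.1 is unaffected. Which of the two figures was intended cannot be settled from the documents.

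**What to change.** Replace the pair with one limit and its correct equivalent in parentheses:

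- if 11.5 mg/dL was intended: corrected serum calcium > 11.5 mg/dL (2.87 mmol/L);
- if 2.65 mmol/L was intended: corrected serum calcium > 10.6 mg/dL (2.65 mmol/L).

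The sponsor should first confirm the intended figure against the response criteria that Appendix A names as its basis.

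The cost is a one-line amendment: a check of the source, written confirmation of the change, and submission by the usual route in Sections 12.2 and 12.5. No visit or test is added.
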